On the other hand, osteophytes formation at the entheseal regions of the joints in PsA is distinctive feature compared with RA (13). The formation of osteophytes is tightly regulated by anabolic pathways, which resembles the pathogenesis of new bone formation in ankylosing spondylitis (AS). Tumor necrosis factor (TNF) inhibition was unable to halt the structural progression in AS patients (14-16), it also lacked efficacy in stopping the progression of osteophytes in PsA patients (17). Inhibition of IL-17 by secukinumab was effective in the treatment of both AS (18) and PsA (12). Secukinumab also decreased the rate of radiographic joint damage regarding to erosion and joint space narrowing (12). However, it is unknown if it has any effect in the progression of osteophytes. In an animal model, although over-expression of IL-17 alone failed to induce entheseal and periosteal bone formation, inhibition of IL-17 leaded to significant reduction of such bone formation in an IL-23 overexpression model (19). Moreover, IL-17A accelerates bone formation by stimulating the proliferation and osteoblastic differentiation of mesenchymal progenitor cells after injury (20). It is worth exploring if secukinumab could prevent the progression of osteophytes in PsA patients.

Aims and hypotheses to be tested:

Hypothesis

IL-17 inhibition by secukinumab could lead to healing of existing erosion, and prevent progression of osteophytes, and resolution of dactylitis in PsA patients.

Aims

The aim of this randomized, double-blind, placebo-controlled study is to evaluate the protective effects of secukinumab on the healing of joint erosion and prevention of progression of osteophytes in PsA patients using HR-pQCT and US.

Objectives

Primary outcome

Difference in changes in the volume of erosions on metacarpophalangeal joints (MCP) 2-4 measured by HR-pQCT at 24 and 48 weeks between secukinumab and placebo group.

Secondary outcomes

- The percentage of erosions with healing determined using HR-pQCT on MCP 2-4 at 24 and 48 weeks including 1). A decrease in erosion volume of ≥0.4 mm³ from baseline, and 2). The presence of grade 2 osteosclerosis at the margin of erosion.
- 2) Changes in volume and width of erosion using HR-pQCT at 24 and 48 weeks;
- 3) Changes in the height of osteophytes using HR-pQCT at 24 and 48 weeks;
- Marginal osteosclerosis (semi-quantitative and quantitative) using HR-pQCT at 24 and 48 weeks;

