- 5) Changes in joint space volume using HR-pQCT at 24 and 48 weeks

Exploratory outcomes

- 1) Changes in US-parameters in dactylitis, enthesitis and synovitis at 24 and 48 weeks
- 2) Changes in van der Heijde-Sharp score on radiograph at 24 and 48 weeks.
- 3) Changes in patients-reported-outcomes (SF-36, Psoriatic Arthritis Impact of Disease (PsAID)) and functional disability (HAQ) at 24 and 48 weeks
- 4) Changes in biomarkers (Pro-C2, C-Col10, COMP, MCP-1, Dkk1 and sclerostin) at 24 and 48 weeks

Plan of Investigation:

Subjects 120 biologic DMARDs naïve PsA patients attending the outpatient clinic of the Prince of Wales Hospital (PWH), North District Hospital (NDH), Tai Po Hospital (TPH), Queen Elizabeth Hospital (QEH) and Tseung Kwan O Hospital (TKOH) who fulfilled the Classification Criteria for Psoriatic Arthritis (CASPAR), will be recruited. The main inclusion criteria are: 1) ≥18 years old; 2) without severe deformity in MCP joints (MCPJ) which would influence the longitudinal assessment of HR-pQCT; 3) with active disease, which is defined as three or more tender joints and three or more swollen joints, despite previous treatment with nonsteroidal anti-inflammatory drugs, disease-modifying antirheumatic drugs. These 120 patients will be screened for the presence of erosion at the head of MCPJ 2-4 using HRpQCT. The first 40 patients with erosion will be randomised in a 1:1 ratio to secukinumab (n=20) or placebo (n=20) group. Based on a study using high-resolution CT in 41 PsA patients, 41% of the patients had at least one erosion, and 90% of the erosions were in MCPs (5). The resolution of the highresolution CT is 0.4 mm, which is almost 5 folds lower than HR-pQCT (82 µm). Therefore, we estimated that over 1/3 of the PsA patients will have at least one erosion in MCPs. Thus, screening 120 patients using HR-pQCT should be adequate to recruit 40 patients with erosions on MCPJ 2-4.

All study procedures will be performed in PWH after recruitment from non-PWH site.

Randomisation will be performed using a computer-generated randomisation list provided by the hospital pharmacist, using a permuted blocks design with block sizes of 4 and 6. Allocation concealment will be ensured by the use of sequentially numbered, opaque, sealed envelopes. Treatment will be masked to patients and investigators.

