The patients will be randomly assigned to the secukinumab group or placebo group. Patients will be followed-up at weeks 2, 4 and then every 12 weeks until week 52. Patients will receive subcutaneous placebo or secukinumab 150 mg once a week from baseline for 4 weeks, and then once every 4 weeks from week 4 onwards. The study flow is shown in Figure 1. Changes in the baseline treatment, e.g. the dosage of conventional synthetic DMARDs (csDMARDs) including methotrexate, leflunomide, hydroxychloroquine, or sulfasalazine or the addition of a new csDMARD (individually or in combination), as well as changes in the dosage or the addition of steroids or nonsteroidal antiinflammatory drugs were allowed after week 12 if the patient cannot achieve minimal disease activity (MDA) (Table 1) (see appendix 1 for the treatment protocol). For patients who fulfil the criteria for biologic DMARDs (bDMARDs) (Appendix 2) and are willing to be started on bDMARDs, the code will be broken, and they can either pay out of pocket or can apply for the Samaritan Fund for financial assistance, provided they must household-based pass а financial assessment (http://www.ha.org.hk/visitor/ha visitor index.asp?Content ID=10048&Lang=ENG&Dimension=100). Patients who have started bDMARDs apart from secukinumab will be excluded from the efficacy assessment. Adverse effects will be recorded.

Evaluation of disease activity and severity

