Data processing and analysis Statistical analyses will be performed using the Statistics Package for Social Sciences (SPSS). Data will be analysed in an intention-to-treat manner. Patients who discontinued treatment or violated treatment protocol will be excluded from analysis. Missing data are assumed missing at random and will be treated using a multiple Imputation method (30). Based on the pilot study and our previous experience, the missing data is estimated to be less than 5%. Descriptive statistics will be used for demographic and clinical variables included frequencies, means and standard deviations, median and interquartile range. T-test, Mann-Whitney U test and Chi-square test will be used to evaluate differences in baseline characteristics between secukinumab group and placebo group. Changes of the outcome measurements between groups will be tested using t-test, Mann-Whitney U test, repeated measures analysis of variance (ANOVA) or Chi-square test where appropriate. Multivariate linear or logistic regression will be used to explore the association between the use of secukinumab and outcome measurements adjusting for baseline characteristics. A 2-tailed probability value of p < 0.05 is considered statistically significant.

Reference

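### Whether a patient who starts a biologic stays in the efficacy analysis depends on which biologic it is, and the Treatment and analysis sections disagree on who is kept

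*Combined protocol and SAP*

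**What the plan says.** The Treatment section of the combined protocol and SAP provides a route to a biologic during the trial. For those who meet the Appendix 2 criteria, the text reads: "and are willing to be started on bDMARDs, the code will be broken, and they can either pay out of pocket or can apply". The last words refer to a fund that gives financial help. No permitted agents are listed there, and secukinumab is neither offered nor barred. The rule on analysis follows directly: "Patients who have started bDMARDs apart from secukinumab will be excluded from the efficacy assessment".

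Data processing and analysis contains two further rules, one after the other: "Data will be analysed in an intention-to-treat manner", and then "Patients who discontinued treatment or violated treatment protocol will be excluded from analysis". The same section plans regression models to "explore the association between the use of secukinumab and outcome measurements", adjusted for baseline characteristics.

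The primary outcome is the difference in change in erosion volume "measured by HR-pQCT at 24 and 48 weeks between secukinumab and placebo group". On sample size, the plan says: "The first 40 patients with erosion will be randomised in a 1:1 ratio to secukinumab (n=20) or placebo (n=20) group".

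**The concern.** The rule in the Treatment section is a post-randomisation exclusion that depends on which biologic a patient starts. It can also act differently in the two arms, because the choice is made after unblinding. A patient who learns that they were on placebo may choose secukinumab, and this sentence would not exclude them. A patient who learns that they were already on secukinumab and wants a different biologic will start another agent and be dropped.

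The two sections then give different answers for the placebo patient who starts secukinumab. The Treatment rule and the intention-to-treat statement keep that patient. The discontinuation rule may remove them, since they have left their assigned treatment. Nothing says which rule takes precedence, or what happens to scans taken before or after the switch.

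At stake is who enters the primary comparison. With 20 per arm, each patient is 5% of an arm (1/20), and the plan leaves the decision open until after codes have been broken.

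**Working it through.** **1. The rules side by side**

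| Patient | Treatment rule, read literally | Intention-to-treat statement | Discontinuation/violation rule |
|---|---|---|---|
| Placebo, starts secukinumab | not excluded | kept | arguably excluded |
| Placebo, starts another biologic | excluded | kept | arguably excluded |
| Secukinumab arm, starts another biologic | excluded | kept | arguably excluded |

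The Treatment rule separates the first two rows by agent alone. No row gets the same answer from all three rules. The last column says arguably because the protocol itself provides the switch, so it is not clearly a violation, though it plausibly counts as discontinuation.

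**2. Inputs**

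- From the documents: 20 per arm, and the significance rule "A 2-tailed probability value of p < 0.05 is considered statistically significant".
- Not in the documents: power, effect size, SD, switching rate and timing of switches. There is therefore no planned figure to reproduce.
- Assumed: a true effect of d = 0.909 SD, which a two-sample t-test with 20 per arm detects with 80% power; s, the share of placebo patients who switch to secukinumab and are retained; and f, the fraction of the full effect they gain by the scan.

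**3. Dilution alone**

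The retained contrast is (1 − s·f) of the original. Power comes from the noncentral t with 38 degrees of freedom and noncentrality 0.909 × (1 − s·f) × √(20/2), with the SD held at 1 and all 40 patients analysed. With no switching, the noncentrality is 0.909 × 3.162 = 2.87 and power is 80%.

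| s | f = 1: contrast, power | f = 0.5: contrast, power | f = 0.25: contrast, power |
|---|---|---|---|
| 10% (2 of 20) | 0.90, 71% | 0.95, 76% | 0.975, 78% |
| 20% (4 of 20) | 0.80, 61% | 0.90, 71% | 0.95, 76% |
| 30% (6 of 20) | 0.70, 50% | 0.85, 66% | 0.925, 74% |

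**4. Net direction when secukinumab-arm switchers are dropped**

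Suppose switching is driven by a standard normal tendency correlated ρ with a worse erosion change. Dropping the top fraction u of the secukinumab arm improves that arm's mean by ρ·m SD, where m = φ(z)/(1 − u) and z is the (1 − u) normal quantile. For u = 10%, m = 0.1755/0.9 = 0.195. For u = 20%, m = 0.280/0.8 = 0.350. With s = 20%, all moving to secukinumab and retained, the ratio to the contrast without switching or exclusion is 1 − 0.2f + ρ·m/0.909.

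| u | ρ | f = 0.25 | f = 0.5 | f = 1 |
|---|---|---|---|---|
| 0 | any | 0.95 | 0.90 | 0.80 |
| 10% | 0.3 | 1.01 | 0.96 | 0.86 |
| 10% | 0.5 | 1.06 | 1.01 | 0.91 |
| 20% | 0.3 | 1.07 | 1.02 | 0.92 |
| 20% | 0.5 | 1.14 | 1.09 | 0.99 |

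The ratio lies on both sides of 1.

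**5. If the discontinuation rule removes all switchers instead**

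With 20% of placebo and 10% of secukinumab patients removed, the ratio is 1 − ρ(0.350 − 0.195)/0.909. That is 0.95 for ρ = 0.3 and 0.91 for ρ = 0.5. The estimate therefore depends on which section is followed.

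**The case against.** The strongest objection is that the exemption may be meant only to stop the secukinumab arm being excluded for taking its assigned drug. No text says that placebo patients are offered open-label secukinumab. This reading is possible. But the sentence follows directly from the provision for unblinding and starting a biologic, and it does not limit the exemption to one arm. The ambiguity therefore stands.

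Second, the discontinuation rule may remove the crossovers anyway. That is fair. A reader might infer from the Treatment section alone that placebo crossovers stay in and the treatment contrast must shrink. The documents support neither step. Retention is unsettled, and the same sentence drops secukinumab-arm patients who move to another biologic, who are probably poor responders, which pushes the other way.

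Third, the full-effect column is an extreme. A switcher has had less than full exposure by the scan, and erosion volume is a structural measure. This stands, and it is why the partial-effect columns are shown.

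Fourth, keeping crossovers in their randomised arm is what intention-to-treat means. This also stands. The fault lies in exempting one agent only, in conflict with another rule, and with no stated handling of the scans.

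Fifth, a reader might take the regression wording to mean coding by drug received. In a two-arm trial it is more naturally shorthand for arm, and as-treated coding is stated nowhere. That part is a matter of clarity only.

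**Conclusion.** The concern holds as a conflict between two sections over who is in the efficacy analysis, caused by a post-randomisation exclusion that depends on the biologic chosen. Following it can bias the primary comparison, and the direction is unknown: under the assumptions shown, the contrast is multiplied by between 0.80 and 1.14 when the Treatment rule is read literally.

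The power losses describe the dilution part only. They run from 2 points (10% switching, quarter effect) to 30 points (30% switching, full effect), starting from an assumed 80%. They are not forecasts, because the documents give no switching rate, timing, effect size or SD, and the text of Appendix 2 was not available for this review. The conflict between the sections does not depend on any of these assumptions.

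**What to change.** Reconcile Treatment with Data processing and analysis. These are changes to the analysis only.

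1. Delete both exclusions from the main analysis. State one rule for any biologic start, secukinumab included, identical in both arms: all randomised patients are analysed in their randomised arm, using every observed scan before and after the switch.
2. Add a supplementary analysis that sets scans after any biologic start to missing, whichever agent was started, and applies the multiple imputation already planned. Scans before the switch stay in.
3. Report biologic starts by arm, agent and week.
4. In the regression, name randomised arm as the explanatory variable.

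The cost is wording in two sections, one extra analysis and one table, with no new data. There are two downsides. The main analysis still contains any crossover dilution, as intention-to-treat implies; only the supplementary analysis addresses it. The supplementary analysis in turn assumes that switchers' scans are missing at random. It may also involve more missing data than the plan's estimate of under 5%, since two switchers among 40 already make 5% (2/40) at a visit after both have switched.

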All possible side effect of the biologic and synthetic DMARDs used the study will be explained to the participants by the research nurse and the treating physician. To monitor the possible side effect, complete blood count, liver function tests and renal function tests will be performed every visit. Chest X-rays will be obtained at baseline and at the end of the study. The treating physician records all nonserious and serious adverse events, all reports of drug exposure during pregnancy, and all reports of misuse and abuse of the Novartis drug, other medication errors and uses outside of what is foreseen in the protocol, if necessary, make treatment adjustments in accordance with the protocol. Serious adverse events are defined as any adverse reaction resulting in any of the following outcomes: a lifethreatening condition or death, a significant or permanent disability, a medically significant event, hospitalization or prolongation of hospitalization, a congenital abnormality, or a birth defect. All adverse events from this trial will be reported to local IRB and Health Authority by the investigator according per requirement as holder of certificate of clinical trial. Any SAEs, reports of drug exposure during pregnancy and reports of Study Drug misuse or abuse, including initial and follow up reports, arising from the Study in subjects exposed to the Study Drug, as soon as it becomes available, but in any event within fifteen (15) calendar days of becoming aware of such information, will be forwarded to Novartis by transmitting it to Novartis Patient Safety team.

Erosion assessment by HR-pQCT

Image acquisition

Metacarpal bone erosion will be assessed at MCP 2-4 of the more severely affected or the dominant hand if both hands are equally affected using a HR-pQCT system (XtremeCT II; Scanco Medical AG, Bruttisellen, Switzerland). This system enables the simultaneous acquisition of CT slices with an isotropic resolution (voxel size) of 82 μ m. HR-pQCT scanning will be performed by a single investigator who is blinded to all the clinical information of the patients. A single examination will be performed for

measurements of MCP 2-4. An anteroposterior scout view will be used to define the region of interest (ROI). The scan region will be 80 slices distal and 242 slices proximal of the upper margin of the head of MCP3. Scan time will be around 8 min per patient and scan (8). The scans will be performed at baseline, 24 and 48 weeks.

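### The definition of a serious adverse event starts from a reaction rather than an event, so read literally a serious event judged unrelated escapes the 15-day forwarding to the manufacturer

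*Combined protocol and SAP*

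**What the plan says.** All of the reporting text is in Safety Data Collection and Reporting.

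- **Recording.** "The treating physician records all nonserious and serious adverse events". Nothing here depends on relatedness.
- **Definition of serious.** "Serious adverse events are defined as any adverse reaction resulting in any of the following outcomes", followed by the list of serious outcomes (death, hospitalisation, disability and so on).
- **IRB and regulator.** "All adverse events from this trial will be reported to local IRB and Health Authority by the investigator", in line with the applicable requirements. No seriousness or relatedness condition is set, and no deadline is given.
- **Manufacturer.** SAEs, together with reports of drug exposure in pregnancy and of misuse or abuse, are forwarded to the manufacturer's safety team when they are "arising from the Study in subjects exposed to the Study Drug", and "in any event within fifteen (15) calendar days of becoming aware of such information".

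Two other places bear on the point. Under Plan of Investigation, "Treatment will be masked to patients and investigators". Under Treatment, for patients who qualify for a biologic DMARD and are willing to start one, "the code will be broken".

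**The concern.** In ordinary safety usage an adverse event is anything untoward that happens to a participant, and an adverse reaction is one attributed to a drug. Building the seriousness definition on the second term makes the SAE label depend on an opinion about cause. Serious events are normally collected and sent on regardless of that opinion, because a single treating physician, masked and seeing one case, is poorly placed to recognise an unexpected drug effect. Patterns become visible only when reports are pooled, and the manufacturer's safety team is one place where that happens. If events judged unrelated are withheld from that team, an unrecognised drug effect could reach it late or not at all.

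**Working it through.** No arithmetic applies. The point turns on wording, and the documents give no rate or SAE-based figure to reproduce. The check is to follow one case through the rules: a patient is hospitalised, and the treating physician judges the event unrelated to any drug.

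1. **Is it recorded?** Yes. The recording rule covers every adverse event, serious or not.
2. **Is it an SAE?** It has a listed outcome (hospitalisation), but the definition also requires a reaction. Read literally, an event judged unrelated fails that condition, so it is not an SAE.
3. **Is it reported to the IRB and Health Authority?** Yes. That rule covers all adverse events and does not use the SAE label. The documents attach no time limit to it.
4. **Is it forwarded to the manufacturer within 15 calendar days?** Not under the literal text. The forwarding rule lists SAEs, pregnancy exposures, and misuse or abuse. The event fails the first at step 2 and is neither of the others. This is the only reporting deadline stated in the section, so the event loses its only stated time limit as well as that recipient.
5. **Can the causal condition be applied consistently?** The documents do not define a reaction, name who judges relatedness, give criteria, or say which drug the reaction must be to. Patients may also be taking methotrexate, leflunomide, hydroxychloroquine, sulfasalazine, steroids or NSAIDs, with changes permitted after week 12, and the judgement is normally made without knowing the allocation. Two physicians could classify the same hospitalisation differently, and both would be within protocol.
6. **Does correcting the one word settle the forwarding?** Not fully. The limit to subjects exposed to the Study Drug is a separate clause and would remain. Study Drug is not defined, so it is unclear whether masked patients, or patients on placebo, fall inside it.

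The gap is therefore confined to two things: the SAE label, and the 15-day route to the manufacturer.

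**The case against.** The strongest reply is that this is loose drafting and not a causal filter. The section uses side effect, adverse event and adverse reaction without distinguishing them, the definition itself counts a medically significant event among the outcomes of a reaction, and no relatedness procedure is described anywhere. A sensible site might well report every serious event. That is plausible, but it is a reason to correct the word, because sites follow the text as written. The reply that such events still reach the IRB and Health Authority is right and stands; it limits the harm without replacing the manufacturer route.

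Three stronger readings are tempting, and the documents do not support them.

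- **Events on known placebo can never be SAEs.** The definition names no drug, and placebo patients may take conventional DMARDs, steroids or NSAIDs, so a serious reaction to one of these meets the wording. Allocation is masked, and the only code break described accompanies a move to a biologic, so known placebo arises in few situations. Any exclusion of placebo patients from forwarding would come from the exposure clause and not from the word reaction.
- **The comparison of SAEs between arms is biased.** Data processing and analysis specifies no safety analysis and no SAE table, so the plan contains no such comparison to distort.
- **Each reclassified event shifts an arm by 5 percentage points.** With 20 patients per arm, 1/20 = 5%, but that is true of any one patient in an arm of 20 and says nothing about how often reclassification would occur.

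**Conclusion.** The point holds in a limited form. The definition is inconsistent with the sentences around it, and followed literally it removes the SAE label and the 15-day forwarding from serious events judged unrelated. It does not remove them from recording or from reporting to the IRB and Health Authority.

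The size is unknown, since it depends on how many serious events occur and what share is judged unrelated, and the documents give neither. The conclusion assumes that reaction carries its usual causal meaning and that sites apply the definition as written. If they read it as event, nothing is lost in practice and only the wording needs correction. The primary HR-pQCT outcome is not affected. The change should be made, because it is cheap and closes a gap in a stated safety rule.

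**What to change.** In Safety Data Collection and Reporting:

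1. Base the SAE definition on *any adverse event, whether or not considered related to study drug*, keeping the existing list of serious outcomes.
2. Record relatedness as a separate field, so that it describes an event without deciding whether the event is serious.
3. Apply the existing 15-day forwarding to all SAEs so defined.
4. Define Study Drug, and state whether the exposure clause covers patients whose allocation is still masked and patients on placebo. Without this, the first change leaves the scope of forwarding open.

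The cost is a few sentences in the protocol, one field on the adverse event form and a few more reports to forward. No dose, visit, endpoint or sample size changes.

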Exclusion criteria are: 1) limited in ability to perform usual self-care, vocational, and avocational activities; 2) pregnancy; 3) previous therapy with biologic; 4) the presence of active inflammatory diseases other than PsA; 5) active infection in 2 weeks before randomization or a history of ongoing, chronic, or recurrent infections including tuberculosis; 6) history of hepatitis B & C; 7) history of malignant disease within the past 5 years (excluding basal cell carcinoma or actinic keratosis, in-situ cervical cancer, or non-invasive malignant colon polyps); 8) contraindications to secukinumab. The concomitant use of oral glucocorticoids (at a dose of \leq 10 mg per day of prednisone or its equivalent) and methotrexate (at a dose of \leq 25 mg per week) are permitted, provided that the dose will be stable.

The study will be approved by the Ethics Committee of the Chinese University of Hong Kong. Written informed consent will be obtained from all participants according to the Declaration of Helsinki and ICH-GCP guidelines.

Methods This is a 52-week, randomized, placebo-controlled, double-blind study. PsA patients will be randomised to either secukinumab or placebo group. All patients will be evaluated and treated according to the following protocol.

Study design

Treatment

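### The plan declares intention-to-treat but then excludes randomised patients who stop or violate treatment, so the primary erosion-volume comparison as written is not intention-to-treat

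*Combined protocol and SAP*

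**What the plan says.** Data processing and analysis states "Data will be analysed in an intention-to-treat manner". The sentence that follows is "Patients who discontinued treatment or violated treatment protocol will be excluded from analysis". The same paragraph assumes data are missing at random, plans multiple imputation, and expects less than 5% missing data.

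The Treatment section adds a second rule: "Patients who have started bDMARDs apart from secukinumab will be excluded from the efficacy assessment". The route to it is that patients who meet the biologic criteria and "are willing to be started on bDMARDs, the code will be broken, and they can either pay out of pocket" or apply for financial assistance.

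The trial is small: "The first 40 patients with erosion will be randomised in a 1:1 ratio to secukinumab (n=20) or placebo (n=20) group". The primary outcome is the between-group difference in change in erosion volume at 24 and 48 weeks. On imaging, the HR-pQCT section says "The scans will be performed at baseline, 24 and 48 weeks".

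No section of the available text names separate analysis sets, says which set is primary, or labels either exclusion as a sensitivity analysis.

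**The concern.** Intention-to-treat keeps every randomised patient in the assigned arm. A rule that drops patients for stopping treatment or departing from protocol selects on events after randomisation. Both cannot govern the same primary comparison, and an analyst following the text literally would apply the exclusion.

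At stake is the protection that randomisation gives to the primary estimate. Patients who stop treatment, or who move to a biologic because disease control is poor, may differ in erosion change from those who stay. If so, and if this works differently on secukinumab and placebo, the retained groups are no longer comparable. With 20 patients per arm, each excluded patient is 5% of an arm.

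The different scope of the two rules leaves a further gap. The Treatment rule spares patients who start secukinumab. A patient unblinded and then started on open-label secukinumab is therefore not removed by that rule, but might be removed under Data processing and analysis as having discontinued study treatment. The text does not say which applies. It also does not define a violation. The Treatment section refers to Appendix 1 for the treatment protocol, but that appendix is not in the available text.

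**Working it through.** **1. The rules side by side**

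| Place | Who is removed | From what |
|---|---|---|
| Data processing and analysis, declared principle | nobody (intention-to-treat) | – |
| Data processing and analysis, next sentence | those who discontinued or violated treatment protocol | analysis |
| Treatment | those who start a biologic other than secukinumab | efficacy assessment |

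The first row contradicts the second and third. A patient who starts another biologic has probably also discontinued study treatment, so rows two and three probably remove many of the same people. They are still two rules with different triggers and different reach.

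Imputation is planned for missing data. The plan does not say whether excluded patients' values would be imputed, or whether the under-5% figure counts them. Neither can be relied on as a remedy.

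**2. How large could the bias be?**

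The plan gives no figure to reproduce here: no exclusion rate, effect size or SD. Everything below is an assumption used for scale.

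Let q be the share excluded in an arm, and r the correlation between the tendency to be excluded and a poor erosion outcome. With normal variables, the mean of those retained shifts towards the better outcome by r × φ(z)/(1 − q) SD, where z is the (1 − q) normal quantile. The bias is the difference between arms.

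- q = 0.30: z = 0.524, φ = 0.3477, and 0.3477/0.70 = 0.4967.
- q = 0.05: z = 1.645, φ = 0.1031, and 0.1031/0.95 = 0.1086.
- Difference: 0.4967 − 0.1086 = 0.3881.
- r = 0.3 in both arms: 0.3 × 0.3881 = 0.12 SD.
- r = 0.5 in both arms: 0.5 × 0.3881 = 0.19 SD.
- r = 0 in both arms: 0.
- 30% in each arm with r = 0.5 in both: 0.
- 30% in each arm, r = 0.5 in one and 0 in the other: 0.5 × 0.4967 = 0.25 SD. Equal rates alone therefore do not protect the comparison.

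If the heavier exclusion of poor outcomes falls on placebo, the bias runs against secukinumab. If it falls on secukinumab, the bias runs in its favour.

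A simulation of 20 per arm with no treatment effect, excluding 10% of one arm and 30% of the other, gave a type I error of 5.0%, 5.7%, 7.9% and 11.1% for r = 0, 0.3, 0.5 and 0.7.

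**3. Does keeping everyone gain power?**

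Assume one value per patient and a two-sided 5% t-test. The effect detectable with 80% power at 20 v 20 is 0.909 SD.

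- Excluding 30% of one arm (6 of 20) and 5% of the other (1 of 20) leaves 14 v 19. Power for 0.909 SD is 71%.
- Keeping all 40 with scans as observed: suppose 30% of placebo patients start an equally effective biologic at week 24. Dilution at week 48 is 0.30 × 0.909 × 24/48 = 0.136 SD. The remaining effect is 0.909 − 0.136 = 0.773 SD, and power is about 66%.
- If they start at baseline, dilution is 0.30 × 0.909 = 0.273 SD. That leaves 0.636 SD, and power is about 50%.

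On these assumptions, keeping everyone does not raise power. The case for the change rests on bias alone.

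**The case against.** The strongest reply is that the exclusion sentence was meant to describe a secondary per-protocol analysis, and that few patients would be affected. Nothing in the available text supports the first part, and no rate is given for the second.

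Several narrower objections do stand, and they limit what a reader might otherwise infer.

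- **That a violation is nowhere defined.** Appendix 1 is cited for the treatment protocol and may define it. All that can be said is that the available text does not.
- **That the background-dose rules conflict.** The exclusion criteria require stable methotrexate and glucocorticoid doses. The Treatment section and the study-flow footnote allow adjustment after week 12, in the former for patients not in MDA. Read together, they largely settle what is permitted on trial.
- **That the exemption for secukinumab is a deliberate loophole.** Secukinumab is itself a biologic, so the wording may only keep the rule from excluding the whole active arm. How open-label secukinumab after unblinding is analysed is still not stated.
- **That patients choose exclusion knowing their arm.** Meeting the criteria and being willing to start come before the code break. Only the choice of agent could follow it, and the documents do not say when that choice is made.
- **That exclusion is wrong because it costs power.** On the assumptions above, as-observed analysis of all 40 can have less power than exclusion.

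**Conclusion.** The contradiction stands on the text alone and must be fixed before analysis, because it decides who enters the primary comparison. As written, that comparison is per-protocol in effect while labelled intention-to-treat. The second, overlapping exclusion differs in scope and is not reconciled with the first.

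The size of any bias is unknown. About 0.12 to 0.19 SD follows from assumed exclusions of 30% v 5% with r of 0.3 to 0.5. It can run in either direction, and it is zero if exclusion is unrelated to outcome. Without an SD for erosion-volume change it cannot be put into mm³. A reader might infer that the result will be biased, or biased in favour of secukinumab. The documents support neither, since they give no exclusion rates, no reasons by arm, and no link between exclusion and erosion volume.

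**What to change.** - Define one primary analysis set: all randomised patients, in their assigned arm. Remove both exclusions as rules for the primary analysis.
- State that the week-24 and week-48 scans, already scheduled, are still obtained after study drug stops. Impute only scans that are truly missing.
- Prespecify one primary handling of scans taken after a biologic start: either as observed, or set to missing and imputed. The other becomes a sensitivity analysis. The choice is the investigators'.
- Keep the exclusions only as a labelled per-protocol sensitivity analysis. Give it one definition that reconciles the two sections and covers patients who start open-label secukinumab after unblinding. Apply it blind to treatment and outcome where possible.
- Report the numbers and reasons excluded, by arm.

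The cost is mostly wording, plus obtaining scheduled scans from patients off study drug. Each handling has a downside. As-observed use may dilute the contrast: power is about 66% rather than 80% for a 0.91 SD effect in the assumed case of 30% of placebo patients starting an equally effective biologic at week 24. Setting scans to missing rests on the missing-at-random assumption and may exceed the plan's under-5% estimate: 0.30 × 20 = 6 patients, and 6/40 = 15%.
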